6.12.2 Laboratory Test

Laboratory data will be summarized by presenting summary statistics of raw data and change from baseline values (means, medians, standard deviations, ranges). For quantitative laboratory parameters, both actual values and change from baseline values will be summarized at each visit.

Shift tables will be presented, in which, lab test results at baseline and post-baseline visit will be classified into below (<LLN), within (\geq LLN and \leq ULN), and above (>ULN) normal ranges. Subject incidences (n and %) will be presented for the shift from baseline to the post-baseline visits.

Note that the analysis window will be applied for the visits.

A complete laboratory data listing, including hematology, biochemistry, and urinalysis will be provided for all subjects.

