12.3 Clinical Laboratory Measurements

Blood and urine samples for clinical safety laboratory tests will be collected at the time points described below. Investigators may have additional laboratory tests performed for the purpose of planning treatment administration or following AE or abnormal laboratory values.

The site will process and ship blood and urine samples per central laboratory instructions. A central laboratory or designee will analyze blood and urine samples and provide results for the clinical safety laboratory tests.

Clinical laboratory testing may be performed locally, if necessary, with prior approval from Allakos. The site will strive to use the central laboratory whenever possible.

For any laboratory test value outside the reference range, the Investigator will determine clinical significance: Not Clinically Significant (NCS) or Clinically Significant (CS). An abnormal laboratory value should be deemed CS if any of the following conditions are met:

- The abnormality suggests a disease and/or organ toxicity that is new or has worsened from baseline.
- The abnormality is of a degree that requires additional active management, e.g., change of study drug dose, discontinuation of the study drug, close observation, more frequent follow-up assessments, or further diagnostic investigation.

Therefore, a clinically significant laboratory value is a lab test value that indicates a new disease process, an exacerbation or worsening of an existing condition, or requires further action to be taken.

For any laboratory test value outside the reference range that the Investigator considers clinically significant, the Investigator will:

- Repeat the test to verify the out-of-range value.
- Follow the out-of-range value to a satisfactory clinical resolution.
- Record as an AE any laboratory test value after start of study drug that:
 - The Investigator considers clinically significant.
 - Requires a subject to be discontinued from the study.
 - Requires a subject to receive treatment.

Blood will be obtained for CBC with differential as described in Section 12.1.9.

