14.11 Study Withdrawal Criteria

A subject's participation in the study will be discontinued in the event that:

- Occurrence of an exclusion criterion, which is clinically relevant and affects the subject's safety, if discontinuation is considered necessary by the Investigator and/or Sponsor.
- Rebounding of eosinophil counts to $>1500/\mu\text{L}$ in subjects who entered the study with eosinophil levels $>1500/\mu\text{L}$ and whose eosinophil counts were initially suppressed after study drug, as assessed by the Safety Monitor, may be withdrawn from the study at the instruction of the Medical Monitor.
- Serum transaminases (ALT and/or AST) $>3 \times \text{ULN}$ and total bilirubin $>2 \times \text{ULN}$ (confirmed by repeat) without an alternative explanation.
- Elevation of ALT or AST $>3 \times \text{ULN}$ (confirmed by repeat) with the appearance or worsening of symptoms felt by the Investigator to be potentially related to hepatic inflammation, such as fatigue, nausea, vomiting, right upper quadrant pain or tenderness, fever, and rash.

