Statistical Analysis Plan – Version 2

18 September 2023

| sessme |
|------------|
| sessm |
| sessn |
| sess |
| ses |
| s |
| v 2 |
| 7. |
| - |
| < |
| ن |
| of |
| - |
| 0 |
| |
| _ |
| Q |
| Ð |
| 4 |
| 2 |
| C) |
| |
| |
| |
| |
| |
| |
| |
| _ |
| - |
| e 1 |
| le 1 |
| ble 1 |
| able 1 |
| Table 1 |

| Table 1 Schedule of Assessments | ssessment | s | | | | | | | | | | |
|--|-----------------------|---|--------------------|---------------------|-----------------------|---|---------------------|---------------------|--|-------------------------|--------------------------------|---|
| Assessment/Procedure Description | Screening | | | Do | uble-Blind T (12 v | Double-Blind Treatment Period (12 weeks) | riod | | | | Follow-Up Period (12 weeks) | P |
| | ~Day -14 (2 weeks) | Day 1 ¹ (±3 days) Baseline | Day 8 (±3 days) | Day 15 (±5 days) | Day 29 (±5 days) | Day 43 (±5 days) | Day 57 (±5 days) | Day 71 (±5 days) | Day 85 (±5 days) | Day 99 (±5 days) | Day 141 (±5 days) | Day 169 (±5 days) |
| | Week -2 | Week 0/ Dose 1 | Week 1 Visit | Week 2/ Dose 2 | Week 4/ Dose 3 | Week 6/ Dose 4 | Week 8/ Dose 5 | Week 10/ Dose 6 | Week 12/ Dose 7 | Week 14/ Follow-up 1 | Week 20/ Follow-up 2 | Week 24/ Follow-up 3/EOS ² |
| Informed consent | x | | | | | | | | | | | |
| Demographics | х | | | | | | | | | | | |
| Medical History | Х | Х | | | | | | | | | | |
| Detailed previous diagnosis and treatments review ³ | Х | | | | | | | | | | | |
| Prior/concomitant medications | Х | Х | х | Х | Х | х | Х | х | Х | Х | X | Х |
| Body weight and height ⁴ | х | х | х | Х | х | х | х | х | х | Х | Х | Х |
| Vital signs ⁵ | Х | х | х | Х | Х | х | Х | х | Х | Х | Х | Х |
| 10-lead or 12-lead ECG ⁶ | х | | | | | | | | | | | |
| Complete physical exam ⁷ | Х | | | | | | | | | | | |
| Symptom-directed physical exam ⁷ | | Х | х | Х | Х | Х | Х | Х | Х | Х | Х | Х |
| vIGA score and dermatologic assessment ⁹ | Х | X | | X | X | x | x | x | Х | Х | Х | Х |
| EASI ⁹ | Х | х | | х | х | х | х | х | Х | Х | Х | Х |
| 6 | X | X | | X | X | X | X | X | X | X | X | X |
| 9 | х | х | | X | х | х | X | х | Х | X | X | Х |
| 8,9 | ~ | | | Complete | daily from | screening t | hrough Day | / 169 or 84 | omplete daily from screening through Day 169 or 84 days post last dose | st dose | | ~ |
| 6 | Х | х | | Х | Х | х | х | х | Х | Х | Х | Х |
| Allakos Inc. | | | | | Page 17 of 55 | 55 | | | | | C | Confidential |

Protocol AK002-018

Statistical Analysis Plan-Version 2

18 September 2023

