5.2 Visit Window and Unscheduled Assessments

Data collected for study assessments provide information on the status of the subject at a given time point. Assessments will be slotted into analysis windows to allow summaries to be performed for subjects with similar study drug exposure. The analysis windows are described in Table 1 by the target study days (see Table 2) of the planned visits. For example, for visit description Day 8, the window is ± 3 days of the visit description.

In the event of multiple values from unscheduled or early termination assessments within a single analysis window, the value closest to the scheduled visit target study day will be used for analyses. If 2 values tie as closest to the time point (for example, 1 value is before and the other value is after the time point), then the later value will be selected. Data collected at all visits will be included in the data listings with visit presented as reported by the site.

eDiary daily results (ppNRS) will be summarized by Study Week as outlined in Table 2.

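### Laboratory shifts are tabulated only by visit window, with no shift to each subject's worst post-baseline value and no counts at the liver-test multiples the protocol names

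*SAP*

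**What the plan says.** SAP 6.12.2 classifies each laboratory result as below, within or above the normal range and reports the shift per visit: "Subject incidences (n and %) will be presented for the shift from baseline to the post-baseline visits". It then adds: "Note that the analysis window will be applied for the visits".

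The windows come from SAP 5.2, which is written for all assessments: "Data collected for study assessments provide information on the status of the subject at a given time point". Where a window holds several values from unscheduled or early termination assessments, "the value closest to the scheduled visit target study day will be used for analyses"; on a tie, "then the later value will be selected".

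The five laboratory tables in SAP Appendix 2 (14.3.2.1 to 14.3.2.5) are all by visit. None uses a worst post-baseline value, a CTCAE grade or a multiple of the upper limit of normal (ULN). Protocol 16.7.3 likewise asks for shifts at each post-baseline time point.

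Protocol 12.3 tells the investigator, for a clinically significant out-of-range result, to "Repeat the test to verify the out-of-range value". It also requires such a result to be recorded as an adverse event. Protocol 14.11 names ALT/AST above 3 x ULN and total bilirubin above 2 x ULN, "confirmed by repeat) without an alternative explanation".

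**The concern.** Picking the value nearest a calendar date is reasonable for describing a time course. A safety reader also asks a different question: how many subjects in each arm ever had an abnormal value, and how far out of range was it? The planned laboratory tables cannot answer that.

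There are three gaps:

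- A repeat drawn in the same window can take the place of the abnormal value that prompted it.
- An unscheduled value on a day outside every window belongs to no visit and so enters no laboratory table.
- With three classes, 1.1 x ULN and 10 x ULN fall in the same shift cell, although protocol 14.11 distinguishes 3 x ULN (ALT/AST) and 2 x ULN (bilirubin).

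The SAP treats adverse events differently. Section 6.12.1 takes the most severe grade when a subject reports the same preferred term more than once.

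**Working it through.** The plan states no figure to reproduce. The check applies the 5.2 rule to the schedule in SAP Table 1.

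**Inputs.** Post-baseline chemistry and CBC visits with their own window: Days 15, 29, 43, 57, 71, 85, 99, 141 and 169, each ±5 days. Day 8 (±3) has no scheduled chemistry or CBC. Rule: closest to target, later on a tie.

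**1. When a repeat displaces an abnormal value.** Let the abnormal draw be s days from target (−5 to +5) and the repeat k days later. The repeat is selected if it lies in the window (s + k ≤ 5) and is no farther from target (|s + k| ≤ |s|).

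- If s ≥ 0, then |s + k| > |s| for every k ≥ 1. A draw on or after the target day is never displaced by a later-day repeat.
- If s < 0, the condition reduces to k ≤ 2|s|.

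| Abnormal draw relative to target | Repeat delays that displace it |
|---|---|
| −5 days | 1–10 days |
| −4 days | 1–8 days |
| −3 days | 1–6 days |
| −2 days | 1–4 days |
| −1 day | 1–2 days |
| 0 to +5 days | none |

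Example: the Day 43 window is Days 38–48. A value on Day 39 has s = −4, so a repeat on any of Days 40–47 is used instead. By contrast, a value on Day 29 followed by a repeat on Day 31 stays in the table.

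The documents give no distribution of visit offsets or repeat delays. *Assuming* all 11 offsets and all delays of 1–7 days are equally likely, displacement occurs in 7 + 7 + 6 + 4 + 2 = 26 of 77 combinations (34%). With delays of 1–3 days it is 3 + 3 + 3 + 3 + 2 = 14 of 33 (42%). These figures illustrate the rule and do not predict this trial.

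**2. Days that lie in no laboratory window (Day 2 to Day 174).**

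- Up to Day 104: Days 2–9 (8 days), plus six gaps of 3 days (21–23, 35–37, 49–51, 63–65, 77–79, 91–93) = 8 + 18 = 26 of 103.
- After Day 104: Days 105–135 (31) and 147–163 (17) = 48 of 70.
- Total: 74 of 173 (43%). Counting the Day 8 window removes Days 5–9, leaving 69. Treating Days 2–4 as part of the Day 1 window leaves 66.

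**3. Dependence on how 5.2 is read.** Section 5.2 does not say whether a scheduled value competes with an unscheduled one. If they compete, step 1 applies. If the scheduled value always takes precedence, step 1 falls away, but an abnormal unscheduled value in a window that already has a scheduled result is then the one left out. Either way one value per window is tabulated, and step 2 is unchanged.

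**The case against.** The case against is substantial, and much of it stands.

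- A reader might infer that an efficacy rule was carried over to safety by mistake. It was not: 5.2 is general, 6.12.2 invokes it expressly, and by-visit shifts follow protocol 16.7.3.
- A reader might infer that serious abnormalities appear in no table. The documents say otherwise. Values that are clinically significant, need treatment or lead to discontinuation are adverse events under protocol 12.3, so they reach the treatment-emergent tables by arm and severity. Every value is also listed.
- A confirmed elevation does not disappear. If the repeat confirms it, the repeat is itself above ULN and the subject still shifts to the high class. Displacement removes only abnormalities that the repeat does not confirm.
- The 43% might be read as the share of results lost. It is calendar coverage on days with no scheduled chemistry or CBC. The Day 141 and Day 169 visits, moreover, do not apply to subjects who enter the open-label extension (OLE).
- The by-visit summaries report ranges, so the largest *selected* value at each visit is visible.
- Safety in this proof-of-concept study rests mainly on adverse events and has no formal inference.

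The adverse event route does not close the gap entirely. Values not judged clinically significant never become adverse events. Under protocol 11.3 and 12.1.9, differential counts after the first dose are withheld from investigator and sponsor until database lock, so the investigator ordinarily cannot judge them unless the Safety Monitor escalates. The same Safety Monitor may request unscheduled CBCs, which can fall between windows. Listings preserve these values but do not compare arms.

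**Conclusion.** The point holds as a limited gap in the safety tables. Laboratory shifts are by visit only, so transient abnormalities, values not judged clinically significant and blinded differential counts receive no any-time laboratory comparison by arm. The three classes also cannot show the ALT/AST and bilirubin multiples named in protocol 14.11.

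Displacement by a repeat is possible but conditional. It needs a draw before the target day, a repeat in the same window no farther from target, and a reading of 5.2 in which scheduled and unscheduled values compete. The loss of between-window unscheduled values from the laboratory tables does not depend on that reading.

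How many subjects would be affected cannot be estimated from the documents, because they give no rate of repeats or unscheduled draws. Nothing here touches the efficacy analysis or suggests that clinically significant events would go unreported. It is a cheap improvement.

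**What to change.** Keep the by-visit shifts that protocol 16.7.3 specifies, and add to SAP 6.12.2 (alongside Tables 14.3.2.3 and 14.3.2.4):

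1. A shift from baseline to each subject's worst double-blind post-baseline value, highest and, separately, lowest, using all scheduled, repeat and unscheduled results without windows.
2. Counts by arm of subjects above the ALT/AST and bilirubin multiples of ULN already stated in protocol 14.11.
3. One sentence in 5.2 saying whether a scheduled value competes with an unscheduled value in the same window.

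The cost is SAP wording and some programming; no new data are needed. Abnormality counts will be somewhat higher than in the by-visit tables. Worst-value counts also rise with the number of samples per subject. Subjects who do not enter the OLE have two further laboratory visits, and unscheduled CBCs may be requested by a Safety Monitor who sees differentials that the drug is expected to change. Footnote this dependence, or limit the worst-value tables to a common period such as through Day 99.

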6.12.3 Vital Signs, Height and Weight, and Other Safety Measures

Vital signs will be summarized by presenting summary statistics of raw data and change from baseline values (means, medians, standard deviations, ranges) for each visit (per analysis window) and time point. A data listing will include vital signs from all visits.

6.12.4 Electrocardiogram

Incidence of the Investigator's overall assessment (normal, abnormal – not clinically significant, and abnormal – clinically significant) will be summarized.

6.12.5 Physical Examination

New or worsening symptoms in the symptom-directed physical exams will be included in the by -subject data listing.

6.12.6 Analysis of Anti-Drug Antibodies

A data listing of anti-drug-antibodies (ADA) results will be provided for all subjects. Number (%) of subjects who are confirmed ADA-positive at any time after receiving study drug and number (%) of subjects who are confirmed ADA-positive at the end of study will be cross-tabulated by their ADA status and titers at predose.

7. Validation

The Clinical Operations and Data Management at Allakos will work with the EDC/Data Management (DM) vendor to ensure that the data collected for the study is of the highest quality possible. The study monitor will be responsible for reviewing and verifying the accuracy of the data recorded on the eCRF directly from source documents at the investigative site. The DM vendor will be responsible for performing edit checks and reviewing all data entered into the electronic database to identify discrepant and/or inconsistent values and to send queries to the clinical sites. The Investigator will be responsible for answering queries about discrepant data and providing electronic signatures to confirm data integrity.

The programming of tables, listings, and figures (TLF) based on the clinical data is outsourced. Allakos seeks to ensure the quality of the reports provided by the CRO in the form of TLF passing a rigorous validation process as follows:

- Derived datasets will be independently reprogrammed by a second programmer. The separate datasets produced by the 2 programmers must match 100%.
- Tables will be independently reprogrammed by a second programmer, and the results from both programs must match.
- Figures will be checked for consistency against corresponding tables and listings or independently reprogrammed if there are no corresponding tables or listings.
- Listings will be checked for consistency against corresponding tables, figures, and derived datasets.

All post hoc analysis, if accepted for inclusion in the study report, will follow the same quality process as stated above. The entire set of TLF will be checked for completeness and consistency prior to delivery to Allakos.

8. References

- International Council for Harmonisation (ICH). Guideline for industry E3, structure and content of clinical study reports, July 1996.
- Food and Drug Administration. E9 (R1) Statistical Principles for clinical trials: addendum: estimands and sensitivity analysis in clinical trials. Guidance for industry, ICH, May 2021.

9.2 Appendix 2: List of Tables, Figures, and Listings

9.1 Appendix 1: Intercurrent Events and Definitions of Prohibited Medication Use and Rescue Medication/Treatment for AD Symptoms

Intercurrent events (ICE) are considered to potentially confound the efficacy outcomes of the study and are defined as follows:

- Premature discontinuation from the double-blind portion of the study for any reason
- Use of prohibited medications during the study
- Use of rescue medication/therapy for symptoms of AD

Prohibited medications are defined as therapies that should not be taken during the course of the study either because of a potential impact on the assessment of efficacy and/or subject safety. Rescue medications/treatments are defined as any therapy or treatment taken during the course of the study for the specific purpose of alleviating AD symptoms that may have an impact on the assessment of efficacy and includes: (1) topical medications (including TCS, TCI and crisaborole), (2) systemic medications (including systemic corticosteroids, immunosuppressant, and biologics), and (3) treatments known to impact AD.

The following provides the details of the prohibited medications/therapies for this study:

1) Prohibited medications where route of administration includes topical/transdermal

Topical Corticosteroids (TCS): ATC code D07 High Potency TCS: ATC codes D07AC or D07AD Low or moderate potency TCS: ATC code D07, excluding D07AC or D07AD
Topical calcineurin inhibitors (TCI): where Preferred Term includes tacrolimus, pimecrolimus
Coal tar: ATC code D05AA
Phosphodiesterase-4 Inhibitors (PDEi): ATC code L04AA32 where Preferred Term includes Crisaborole: ATC code D11AH, roflumilast (no topical ATC code) or apremilast gel

2) Prohibited systemic medications (including systemic corticosteroids, immunosuppressants, immunomodulators, and biologics)

Systemic corticosteroids: ATC code is H02 Immunosuppressants or immunomodulators: ATC code is L04 Mycophenolate: ATC code is L04AA06 Methotrexate: ATC code is L04AX Interferons: gamma: ATC code is L03AB where Preferred Terms include interferon gamma, interferonalfa-2b Leukotriene inhibitors: ATC code is R03DC where Preferred Term includes Ibudilast, Montelukast, Pranlukast, and Zafirlukast Oral calcineurin inhibitors: ATC code is L04AD where Preferred Term includes Ciclosporin, Cyclosporin, Tacforius, Tacrolimus, Voclosporin IV immunoglobulins: ATC code is J06B Doxepin: ATC code is N06AA Janus Kinase inhibitors (JAKi): ATC code is L01EJ where Preferred Term includes Delgocitinib, Fedratinib, Pacritinib, Ruxolitinib and ATC code is D11AH with Preferred Term Abrocitinib Phosphodiesterase-4 Inhibitors (PDEi): ATC code L04AA32 where Preferred Term includes apremilast (oral) TNF inhibitors: ATC code is L04AB where Preferred Term includes Adalimumab, Afelimomab, Certolizumab, Etanercept, Golimumab, Infliximab, Opinercept, Ozoralizumab

Note 1: The use of a short course of systemic corticosteroids for a medical condition other than atopic dermatitis, in the event of medical necessity when no alternative non-steroid treatment is available, will be allowed provided that the use is limited to less than 5 days and the therapy is not taken within 28 days of the Day 99 visit.

Note 2: Leukotriene inhibitors: ATC code is R03DC where Preferred Term includes Ibudilast, Montelukast, Pranlukast, and Zafirlukast are permitted during the study provided that doses remain stable throughout the study unless change is required for an unforeseen medical necessity. Initiation of any new leukotriene inhibitor is prohibited.

Biologics:

Agents For Dermatitis, Excluding Corticosteroids: ATC code is D11A where preferred terms include Dupilumab, Tralokinumab

CD20 inhibitors: ATC code is L01F where preferred terms include Obinutuzumab, Ofatumumab

Selective Immunosuppressants: ATC code is L04AA where preferred terms include Abatacept, Abetimus, Alemtuzumab, Anifrolumab, Apremilast, Baricitinib, Begelomab, Belatacept, Belimumab, Belumosudil, Deucravacitinib, Eculizumab, Efalizumab, Emapalumab, Filgotinib, Fingolimod, Inebilizumab, Itacitinib, Natalizumab, Ocrelizumab, Ofatumumab, Ozanimod, Peficitinib, Pegcetacoplan, Ponesimod,

Ravulizumab, Sutimlimab, Teprotumumab, Teriflunomide, Tofacitinib, Upadacitinib, Vedolizumab

Interleukin Inhibitors: ATC code is L04AC where preferred terms include Anakinra, Basiliximab, Bimekizumab, Briakinumab, Brodalumab, Canakinumab, Daclizumab, Guselkumab, Ixekizumab, Netakimab, Olokizumab, Rilonacept, Risankizumab, Sarilumab, Satralizumab, Secukinumab, Siltuximab, Sirukumab, Spesolimab, Tildrakizumab, Tocilizumab, Ustekinumab

Unspecified Immunosuppressants: No ATC code with Preferred Term including Barzolvolimab, Fezakinumab, Fletikumab, Gevokizumab, Gusacitinib, Ladarixin,

Lebrikizumab, Ligelizumab, Mirikizumab, Nemolizumab, Olamkicept, Tabalumab, Tregalizumab

Other Systemic Drugs for Airway Disease: ATC code R03D with Preferred Term including Benralizumab, Mepolizumab, Omalizumab, Reslizumab, Roflumilast, Tezepelumab and ATC code is R03DX with Preferred Term including Rituximab

- 3) The use of prescription emollients or emollients containing additives such as ceramide, hyaluronic acid, urea, or filaggrin are not allowed during the course of the study except as rescue therapy.
- 4) Treatments for Atopic Dermatitis:

The use of ultraviolet A or B (UVA or UVB), psoralen + UVA (PUVA), other phototherapy, or tanning beds is also not permitted during the study. The use of a tanning bed will not be considered rescue therapy.

